Final follow-up assessments, as described above in Visit 2, will be completed after 6 weeks of the tDCS intervention.

At the end of visit 18, we will provide the opportunity for participants to continue tracking their FitBit information for up to additional 3 months. If the participant agrees, we will keep the tracking option available for the study team to track the retention of the intervention. The study team will terminate this tracking service by the end of the retention phase.

Materials for recruitment and study conduct

StimFit_Recruitment_Flier_20200108_clean.pptx

StimFit_Recruitment_Flier_notabs_20200108_clean.pptx

StimFit_Recruitment_letter_20200205_tracked IRB edits_clean.doc

Assessment of Protocol Understanding Form.docx

International Physical activity Questionnaire IPAQ short procedure Q by Q and questions.docx

MOCA.pdf

Stim-Fit_Phone_Screen_2020205_clean.docx

Stim-Fit_tDCS_Eligibility_Questionnaire.docx

The PAR Q.docx

gradCPT Instructions_FrailAdults.docx

N-Back_Instruction.docx

TRAILS_V1.pdf

TRAILS_V2.pdf

Trails_v3_corrected.docx
Digit Span.pdf
Blood Pressure Form_42219.docx
DT Balance Assessment 42219.docx
DT familiarization and sitting assessment 42219.docx
DT gait assessment 42219_AlipgEdit.docx
GDS15.pdf
Height and Weight Form 42219.docx
Medical History Questionnaire_1 71318.docx
Medication Review Form_1 42219.docx
Sociodemographic Form 42219.docx
TUG form 42219.doc
BARSE.pdf
ESES worksheet_exercise_self-efficacy_scale_eses_0.docx
SEW_DUR.pdf
SRQ-Exercise_short.pdf
WHAS Pain Questions.docx
tDCS Blinding Efficacy.docx
tDCS Side Effects Questionnaire.docx
Cognitive Reserve Questionnaire.pdf

Data Analysis and Data Monitoring

Data Analysis

This study will enroll 32 participants. We have conservatively planned for approximately 20% attrition and have thus based our statistical plan on complete datasets of $n = 26$.

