Assessment of feasibility endpoints will be based on sample computations, including the screened to enrolled ratio, retention rate, assurance of blinding, and safety assessment (see above). Adverse events (AE) will be organized according to the MedDRA classification system and reported in each DSMB communication both by MedDRA System Organ Class (SOC) and overall. Both the number of individuals with one or more of AEs within each SOC, as well as the total count of all AEs within each SOC, will be reported. These will be accompanied by point and 95% confidence interval estimates of the proportion of individuals who would experience AEs and the total count of AEs per person-time within each SOC, respectively. The latter computation will acknowledge clustering at the level of the participant by using generalized estimating equations (GEE) in estimation with robust variance estimates used for computing confidence intervals.

We will use variance decomposition to generate estimates of within and between-individual variation in functional outcomes that would potentially be used in a subsequent trial (see above), along with confidence interval estimates for said variance measures, in order to assist in planning of the subsequent study. We will also conduct an exploratory analysis of the mean change in these endpoints using mixed-effects linear regression of all time points, with a random effect included at the participant level in acknowledgement of serial correlation of repeated measures. Dependent variables will be the change in outcomes related to average daily activity from baseline to the six-week post-tDCS follow-up period, as well as the change in laboratory-based functional outcomes from baseline to each planned follow-up visit.

Feasibility outcomes:

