The proposed sample size was motivated by our experience in similar pilot studies, the need to develop a sufficiently detailed profile of the background population and convincing demonstration of the feasibility of our protocols, the anticipated drop-out rate, and the need to make resource and sample size estimations for the subsequent trial. We anticipate, based on prior work, that we will screen between 5 and 15 individuals for each participant enrolled. Enrollment of 32 individuals will allow us to determine within 1 individual the expected number of participants screened to enrolled in the subsequent trial using an 80% confidence interval; similarly, we will be able by the same method to estimate the probability a given participant will complete intervention to within 0.10.

Functional outcomes:

Assuming type-I error probability = 0.05 and cumulative attrition and missingness approximately = 20% (i.e.

evaluable data on 26 participants with complete data, the design will obtain 90% power to detect standardized differences [ratio of mean within-participant difference on endpoints to the standard deviation (SD) of same] of at least 0.41, and 80% power to detect effects of 0.36 or greater.

Our primary functional endpoint is habitual physical activity defined as average daily step counts derived from a FitBit wristband. As no prior study has investigated the change in total steps per week as a result of this type of intervention, we estimate the SD of the intervention-attributable change based on prior data on changes in weekly step counts in other conditions. Given that a prior study of pulmonary rehabilitation demonstrated a SD of 150 steps per week,⁸⁴ we will have 90% power to detect changes as small as 62 steps per week, and 80% power to detect 54 steps per week.

The GPS data will be analyzed by the team at the University of Pittsburgh. The GPS data were downloaded to a secure computer and saved with only the study ID number. Our team will upload the GPS data to the secure server at the University of Pittsburgh. No other identifiable information will be provided to the team at the University of Pittsburgh.

Data Storage and Confidentiality

Data Storage

All data collected for analysis will be de-identified and assigned a unique study number. Data collection forms will be kept in a locked file cabinet in the office of the PI at Hebrew SeniorLife. Data will be entered and stored on a password-protected secure server at HebrewSeniorLife.

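### Enrolling 32 fixes the screened-to-enrolled ratio to within 1 person (80% CI) only if the ratio is about 5; the half-width is about 2.2 at 10 and 3.3 at 15

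*Protocol*

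**What the plan says.** The protocol's Data Analysis section says of the feasibility endpoints: "Assessment of feasibility endpoints will be based on sample computations, including the screened to enrolled ratio, retention rate". Under Feasibility outcomes it gives planning figures. The anticipated ratio is that "we will screen between 5 and 15 individuals for each participant enrolled". The precision claim follows: "Enrollment of 32 individuals will allow us to determine within 1 individual the expected number of participants screened to enrolled in the subsequent trial". The confidence level attached to this claim is 80%. A companion claim is then made: "similarly, we will be able by the same method to estimate the probability a given participant will complete intervention to within 0.10".

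The same paragraph offers resource and sample-size planning for the subsequent trial as one reason for the chosen sample size. No formula, variance model or standard deviation is given for the ratio, and the text does not say which ratio the precision of 1 refers to.

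**The concern.** The sampling error of a screened-to-enrolled ratio grows almost in proportion to the ratio, because rarer enrolment makes the number of screens between enrolments more variable. One absolute precision figure is therefore unlikely to hold over a threefold range of ratios. The protocol states one such figure directly after giving a range of 5 to 15.

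The ratio is a recruitment input for the follow-on trial. If its stated uncertainty is too small, the screening effort and budget for that trial will be planned on a range that is too narrow.

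**Working it through.** **Inputs**
- Enrolled: n = 32 (protocol, Feasibility outcomes).
- Ratio: R = 5 to 15, so the enrolment probability is p = 1/R, from 0.20 down to 0.067 (same place).
- Confidence: 80%. Read as two-sided, z = 1.2816. The protocol does not state sidedness.
- Completion probability, for the companion claim only: about 0.80, from "We have conservatively planned for approximately 20% attrition" (protocol, Data Analysis).

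**Step 1. Identify the method from the companion claim.** The half-width for a proportion is z × √(p(1−p)/n) = 1.2816 × √(0.8 × 0.2/32) = 0.091. This reproduces the stated 0.10 and supports a two-sided 80% normal approximation with n = 32.

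**Step 2. Variance of the ratio.** If each screened person enrols with probability 1/R, the number screened per enrolment is geometric with mean R and variance R(R−1). Its standard error over 32 enrolments is √(R(R−1)/32). Treating 32 as a binomial count out of 32R screened and applying the delta method to 1/p gives the same result: R² × √((1/R)(1−1/R)/(32R)) = √(R(R−1)/32).

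**Step 3. Half-widths, 1.2816 × √(R(R−1)/32)**

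| R | Standard error | 80% half-width | Exact 80% interval (Clopper-Pearson, inverted) |
|---|---|---|---|
| 5 | 0.791 | 1.01 | 4.06 to 6.27 |
| 7.5 | 1.234 | 1.58 | – |
| 10 | 1.677 | 2.15 | 8.00 to 12.68 |
| 12.5 | 2.120 | 2.72 | – |
| 15 | 2.562 | 3.28 | 11.95 to 19.08 |

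The plan's figure is reproduced, after rounding, at R = 5 only. Setting the half-width to 1 gives R(R−1) = 32/1.2816² = 19.48, so R = 4.94.

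**Step 4. The same result seen two other ways**
- Confidence carried by ±1: at R = 10, 1/1.677 = 0.60 standard errors, about 45%; at R = 15, 1/2.562 = 0.39 standard errors, about 30%. Simulating 32 enrolments gave probabilities of 0.81, 0.46 and 0.31 that the estimate lies within 1 of the truth at R = 5, 10 and 15.
- Enrolment needed for ±1, 1.2816² × R(R−1): 33 at R = 5, 148 at R = 10, 345 at R = 15.

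**Step 5. Other interval forms and readings**
- Wilson, log-scale, t and exact intervals are slightly wider: 2.16 to 2.34 at R = 10 and 3.31 to 3.57 at R = 15.
- One-sided 80% (z = 0.8416): 0.67, 1.41 and 2.16 at R = 5, 10 and 15. This exceeds 1 above R of about 7.2.
- Poisson variance (R in place of R(R−1)): 0.51, 0.72 and 0.88. This stays below 1 throughout, but understates the variance by a factor of R−1, that is 4 to 14.
- A standard deviation guessed from the width of the 5 to 15 range: 0.38 to 0.88, depending on how the range is converted.

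**The case against.** The strongest reply is that the fault is a missing qualifier, not a wrong calculation. The figure does come out at R = 5, and the text never says which ratio it refers to. The companion claim is equally unqualified: it holds at 80% completion (0.091) but not at 70% (0.104) or 50% (0.113). Nor does the protocol state a variance model, and two variants stay below 1 over the whole range.

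This goes only part of the way. A claim made immediately after a range of 5 to 15, with no restriction, will be read as covering that range. Neither variant suits the endpoint. Repeated screening with an enrol or not-enrol result gives variance R(R−1), not R. The 5 to 15 range describes uncertainty about the mean ratio, not the spread of individual screening counts.

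Other points limit the weight of the finding, and they stand:
- The understatement depends on R: none at 5, about 1.6-fold at 7.5, and two- to threefold only from about 10 to 15.
- Relative precision is nearly constant, about ±20% at R = 5 and ±22% at R = 15, which is a respectable pilot result.
- The sample size rests on several grounds besides this one. No progression threshold, power figure or endpoint analysis uses this half-width.
- The later SAP names only session completion rates as feasibility outcomes and does not list the ratio. That lowers the importance of the claim but does not correct the protocol.
- The choice among interval methods is secondary: at R = 10 the Wald, Wilson and log half-widths differ by about 0.02.

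**Conclusion.** The precision claim is wrong as written over almost all of the protocol's own range. With 32 enrolled, the 80% half-width is about 1 at a ratio of 5, 2.2 at 10 and 3.3 at 15.

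As an illustration, assume a follow-on trial of 100 participants, a size not taken from the documents. At a ratio of 15, the 80% interval runs from roughly 1,200 to 1,900 screens; a precision of ±1 would imply 1,400 to 1,600.

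The result assumes independent screening outcomes with a common enrolment probability and a two-sided 80% interval. Differences in enrolment between housing sites would normally widen the interval further. The functional-outcome analysis, participant safety and the enrolment target are unaffected. The sentence should be corrected because the protocol uses it in justifying the sample size.

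**What to change.** Replace the sentence in Feasibility outcomes with one that gives the precision by ratio and names the model, for example: with 32 enrolled, and screening outcomes treated as independent, the 80% confidence interval half-width for the number screened per enrolled participant is about 1 if the ratio is 5, 2.2 if it is 10 and 3.3 if it is 15 (roughly ±20 to 22% of the ratio). It would help to state in the same place that the completion-probability figure assumes about 80% completion.

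When results are reported, give the observed ratio with a confidence interval. An exact binomial or negative-binomial interval is suitable and needs only the numbers screened and enrolled.

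The cost is one sentence and a less favourable stated precision. No additional participants or data are needed.

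### The stated 90%/80% power cannot be reproduced: 26 evaluable participants give about 52%/42% at within-participant effects of 0.41/0.36

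*Protocol*

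**What the plan says.** The protocol's Data Analysis section plans on "approximately 20% attrition and have thus based our statistical plan on complete datasets of" 26, out of 32 enrolled (16 per group). Under Functional outcomes, with type I error 0.05, it states that with "evaluable data on 26 participants with complete data, the design will obtain 90% power to detect standardized differences" "of at least 0.41, and 80% power to detect effects of 0.36 or greater". The standardized difference is defined in the same sentence as the "ratio of mean within-participant difference on endpoints to the standard deviation (SD) of same". No test, sidedness, number of repeated measurements or correlation is given.

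The next paragraph turns this into steps. "Our primary functional endpoint is habitual physical activity defined as average daily step counts derived from a FitBit wristband". "Given that a prior study of pulmonary rehabilitation demonstrated a SD of 150 steps per week", the protocol concludes that "we will have 90% power to detect changes as small as 62 steps per week, and 80% power to detect 54 steps per week".

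The SAP (Statistical Methods) analyses daily step count by a two-way repeated-measures ANOVA of change from the two-week baseline to each two-week period, with group, time and their interaction as effects. Both groups receive the counselling (Number of Subjects).

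**The concern.** An effect expressed as a mean difference over the SD of that difference is on the one-sample (paired) scale, so n, alpha and the effect fix the power once sidedness is chosen. With 26 participants, effects near 0.4 on that scale are too small for 90% power.

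This is the only power statement for the primary functional endpoint. The pilot is meant to inform the size of a later trial. A reader who accepts 90% power at 0.41 would think the pilot far more sensitive than it is, and could take a null result as evidence against an effect.

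Two related problems sit in the same text. The step figures are weekly while the endpoint is daily. And a within-participant change mixes the effect of counselling with that of stimulation, so it is not the tDCS-versus-sham contrast that the SAP tests.

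**Working it through.** **Inputs from the documents.** Alpha 0.05; 26 evaluable (32 × 0.8 = 25.6); d = 0.41 for 90% and 0.36 for 80% power; SD 150 steps per week; 1:1 allocation, so about 13 evaluable per arm if dropout is balanced.

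**Where the step figures come from.** 0.41 × 150 = 61.5 and 0.36 × 150 = 54. They are the same standardized effects rescaled, not a separate calculation.

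**Power on the stated inputs.** Noncentral t, df = n − 1, noncentrality d√n. For n = 26: 0.41 × √26 = 2.09 and 0.36 × √26 = 1.84. The two-sided critical value is 2.06, so power has to be near one half or below.

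| Setting | Power at 0.41 (claimed 90%) | Power at 0.36 (claimed 80%) |
|---|---|---|
| n = 26, two-sided | 52.0% | 42.3% |
| n = 26, one-sided | 65.1% | 55.6% |
| n = 32, two-sided | 61.3% | 50.5% |
| n = 32, one-sided | 73.4% | 63.6% |

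A simulation of 200,000 trials (n = 26, two-sided) gave 52.2% and 42.5%.

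**Detectable effect, n = 26.** Two-sided: 0.662 (90%) and 0.572 (80%). One-sided: 0.590 and 0.501.

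**Participants needed for the stated pair.** Two-sided: 65 for 0.41 at 90% and 63 for 0.36 at 80%. One-sided: 53 and 50. The printed pair fits about 64 paired differences (89.8%/81.0% two-sided), which is 2 × 32. Double counting is a possible explanation, but that is inference; the text does not say so.

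**Could repeated measures explain it?** Suppose 0.41/0.36 were scaled to the SD of a single-period change, and m periods with equal correlation ρ were averaged. The claim then needs (1 + (m − 1)ρ)/m ≤ (0.41/0.662)² = 0.384 for 90%, or (0.36/0.572)² = 0.396 for 80%.
- m = 4 (the eight-week follow-up): ρ ≤ 0.18–0.20 two-sided, 0.31–0.35 one-sided.
- m = 3 (the six weeks after tDCS): ρ ≤ 0.08–0.09 two-sided, 0.22–0.27 one-sided.

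Change scores that subtract one shared baseline correlate 0.5 when the raw periods have equal variances and equal correlations: covariance σ²(1 − r) over variance 2σ²(1 − r).

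**Corrected steps at SD 150.** 0.662 × 150 ≈ 99 and 0.572 × 150 ≈ 86 steps per week. Divided by 7, that is about 14 and 12 steps per day, against 62/7 ≈ 9 and 54/7 ≈ 8 as stated.

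**Between arms.** Two-sample t, 13 per arm, df = 24, two-sided: detectable difference 1.33 SD (90%) or 1.15 SD (80%) of a single change score. At 0.41 and 0.36 the power is 17% and 14%. For the repeated-measures ANOVA group effect, multiply 1.326/1.145 by √((1 + (m − 1)ρ)/m):

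| m | ρ (assumed) | 90% | 80% |
|---|---|---|---|
| 3 | 0.5 | 1.08 | 0.94 |
| 4 | 0.5 | 1.05 | 0.91 |
| 3 | 0.9 | 1.28 | 1.11 |
| 4 | 0.9 | 1.28 | 1.10 |

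**The case against.** The protocol names neither a t-test nor a sidedness, and it plans a mixed model of all time points. So the paired two-sided test is a reading. That is fair, but the printed definition of the effect points to the paired scale, and the one-sided version fails too. The figures can be recovered only from inputs the protocol does not give: low correlations among change scores, or scaling to the raw SD with a pre-post correlation near 0.80. The latter contradicts the printed definition.

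The between-arm range depends on an assumed correlation and period count. The SAP's overall approach also mentions baseline-adjusted mixed models, which would be more sensitive. With equal variances and raw correlations of 0.5 to 0.9, covariate adjustment brings the 90% figure to about 0.81–1.04 single-period change SDs, ignoring the degree of freedom spent on the covariate. This stands as a caveat: the range given above applies to the change-score ANOVA that the SAP names for daily steps. Either model leaves detectable effects far above 0.41.

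The weekly unit of the SD of 150 cannot be verified from the documents, because the reference list supplied ends before the cited source. The per-day conversion is therefore conditional on that SD and unit.

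Finally, the consequence is limited. "The proposed sample size was motivated by our experience in similar pilot studies" and by other feasibility and planning needs, the mean-change analysis is called exploratory, and no decision rule uses 0.41 or 0.36. That bears on severity, not on whether the figures are right.

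**Conclusion.** The concern holds. With 26 evaluable participants and alpha 0.05, power is 52%/42% two-sided where 90%/80% is claimed, and no one- or two-sided test with 26 or 32 participants on the stated scale reaches the claim. The detectable within-participant effects are 0.66/0.57, about 60% larger than stated (0.66/0.41 = 1.61; 0.57/0.36 = 1.58), and the step figures carry the same error. This rests on the protocol's own definition of the effect and a two-sided paired t-test.

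The between-arm figures also assume balanced dropout, three or four periods and a change-score correlation of 0.5 to 0.9. Severity is moderate: the figures should be fixed, but the rationale for enrolling 32 does not depend on them.

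**What to change.** In the protocol's Functional outcomes text:

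1. Replace the 0.41/0.36 statement with: *With 26 evaluable participants and two-sided alpha 0.05, a paired t-test has 90%/80% power to detect a within-participant standardized change of 0.66/0.57.*
2. Confirm the SD of 150 and its unit. If it is kept, replace 62/54 with about 99/86 steps per week (about 14/12 steps per day), so that the figure can be read against the daily endpoint.
3. Add: *For tDCS versus sham (repeated-measures ANOVA group effect, 13 evaluable per arm, two-sided alpha 0.05), the detectable difference is about 1.05–1.28 SD (90% power) or 0.91–1.11 SD (80% power) of a single-period change score, assuming three or four two-week periods and a change-score correlation of 0.5 to 0.9.* If the baseline-adjusted model is to be the main one, size that instead and say so.

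If a one-sided test or a single-period SD lay behind 0.41/0.36, state it, with the number of periods and the correlation assumed.

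The cost is two sentences corrected, one added, and less favourable detectable effects. No participants, procedures or SAP analyses change.

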**Study Title: Modulating brain activity to improve goal-directed physical activity in older adults**

**NCIT number: NCT04278560**

**Date of the document: 10/27/2023**

### **Statistical Methods**

Overall approach: Exploratory analyses will be used to assess outcomes distributions, and any necessary transformations (e.g., to combat significant skew) will be performed prior to estimation of mean treatment effects. Said estimation will use mixed effects linear regression of post-intervention within three days after the last brain stimulation session and again within three days after the last behavior session, with random intercepts and slopes to account for serial correlation in repeated measurements on individuals. Models will control for baseline outcomes in analysis of covariance.

Two-way repeated-measures ANOVA will be used to examine the effect of intervention on primary and secondary functional outcomes. The effect of the 10-session tDCS intervention on the primary functional outcome (daily step count) will be analyzed with a two-way repeated-measures ANOVA. The dependent variable will be *the change in average daily step count from the two-week baseline to each two-week study period of the behavioral intervention*. Model effects included group (tDCS, sham), time (two-week period), and their interaction. The effect of intervention on secondary functional outcomes, which will be collected at baseline, after the two-week brain stimulation intervention, and after the behavioral intervention. Dependent variables will be *the changes in each functional outcome from baseline to each follow-up visit*. The model's effects included group (tDCS, sham), time (post-stim, final) and their interaction.

The feasibility outcomes are the completion rates for the brain stimulation sessions and the behavior sessions, respectively. We will use independent t-tests to examine the differences between two study arms.

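### The stated detectable effects of 0.41 and 0.36 SD, and so 62 and 54 steps per week, do not have 90% and 80% power with 26 complete datasets, and they are not effects of tDCS against sham

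*Protocol*

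**What the plan says.** All the power statements are in the protocol, Data Analysis, under Functional outcomes. Type-I error is 0.05, with no statement of one or two sides, and about 20% is allowed for attrition and missing data. The general claim is: "evaluable data on 26 participants with complete data, the design will obtain 90% power to detect standardized differences". The threshold is 0.41 for 90% power and 0.36 for 80%. The standardized difference is defined as the "ratio of mean within-participant difference on endpoints to the standard deviation (SD) of same".

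The next paragraph applies this to steps. "Our primary functional endpoint is habitual physical activity defined as average daily step counts derived from a FitBit wristband". For the SD, "we estimate the SD of the intervention-attributable change based on prior data on changes in weekly step counts in other conditions". The value used is cited to reference 84: "Given that a prior study of pulmonary rehabilitation demonstrated a SD of 150 steps per week". From this the protocol concludes that "we will have 90% power to detect changes as small as 62 steps per week, and 80% power to detect 54 steps per week".

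The SAP, Statistical Methods, makes the dependent variable "the change in average daily step count from the two-week baseline to each two-week study period of the behavioral intervention". On the terms of the model it says: "Model effects included group (tDCS, sham), time (two-week period), and their interaction". It contains no power statement.

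**The concern.** An effect of about 0.4 SD is small for 26 people, and 90% power there looks too good even for a paired comparison. The trial also randomizes 16 per arm to real or sham stimulation and the SAP tests group, so a within-participant effect is not the one that the randomized comparison estimates. Finally, the endpoint is daily while the detectable change is weekly.

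This is the only absolute statement of what the trial can detect on its primary functional endpoint. If it is too optimistic, a null result could be read as stronger evidence against an effect than it is. The trial is also meant to inform the sample size of a subsequent one. The standardized sentence speaks of endpoints in general, so the same error reaches every functional outcome.

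**Working it through.** **Inputs.** From the protocol: type-I error 0.05; 32 enrolled, 16 per arm; 32 × 0.8 = 25.6, rounded to 26 complete datasets, taken as 13 per arm; SD of change 150 steps per week. Assumed: two-sided test.

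**The plan's own figures.** 0.41 × 150 = 61.5, stated as 62; 0.36 × 150 = 54. The last step reproduces, so any error lies in 0.41 and 0.36.

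**Within participant, as the protocol defines the effect.** The normal approximation is d = (z for alpha + z for power) / √n:

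- 90%: (1.960 + 1.282) / √26 = 3.242 / 5.099 = 0.636
- 80%: (1.960 + 0.842) / √26 = 2.802 / 5.099 = 0.549

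The exact noncentral t calculation with 25 degrees of freedom gives 0.662 and 0.572. At an SD of 150 these are about 99 and 86 steps per week, 1.6 times the stated figures.

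**Could another reading rescue 0.41 and 0.36?** All rows are for a paired test at 5%.

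| Reading | Detectable at 90% / 80% (SD) | Power at 0.41 / 0.36 |
|---|---|---|
| n = 26, two-sided | 0.66 / 0.57 | 52% / 42% |
| n = 26, one-sided | 0.59 / 0.50 | 65% / 56% |
| n = 32, two-sided | 0.59 / 0.51 | 61% / 51% |
| n = 32, one-sided | 0.53 / 0.45 | 73% / 64% |

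None does. A two-sided paired test would need 65 participants for 0.41 at 90% power and 63 for 0.36 at 80%.

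**Averaging periods.** The eight-week follow-up could hold four two-week periods. Averaging four changes with common correlation r multiplies the SD by √((1 + 3r)/4). To bring 0.662 down to 0.41 requires (1 + 3r)/4 = (0.41/0.662)² = 0.384, so r = 0.18. For 0.36 it requires (0.36/0.572)² = 0.397, so r = 0.20. The stated pair is therefore reached only if r is about 0.19 or less.

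**tDCS against sham.** For 13 against 13, one two-week period, no baseline adjustment, two-sided 5%, noncentral t with 24 degrees of freedom, the detectable difference is 1.326 SD (90%) and 1.145 SD (80%). Averaging four periods for the group main effect, with non-negative correlation, at best halves this: 0.66 and 0.57 SD at r = 0, still above 0.41 and 0.36.

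**Scale and source.** 62/7 = 8.9 and 54/7 = 7.7 steps per day; 150/7 = 21.4 steps per day. The printed reference list ends at 48, so reference 84 cannot be found in it.

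**The case against.** The strongest defence is repeated measurement. The protocol plans a regression on all time points, and four-period averaging with a correlation near 0.19 would give almost exactly 62 and 54 within participant. But the protocol states neither averaging nor a correlation, and it standardizes by the SD of the difference itself. The defence shows that the figures are not impossible under some model; it does not show that they follow from what is written. It does mean that 0.66 and 0.57 should be labelled as applying to a single change score.

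Second, the protocol never claims power between arms, and the SAP's overall approach adjusts for baseline and uses repeated measures. That stands. The values 1.33 and 1.15 SD illustrate a different contrast and do not recompute the stated claim. The gain from baseline adjustment cannot be quantified from the documents.

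Third, weekly to daily is division by seven and leaves power unchanged, and the missing reference is not peculiar to this SD: citations 51, 52, 67 and 73 also lie beyond the printed list. Both points are fair. These are matters of clarity and traceability, not separate power errors.

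Fourth, this is a pilot. The sample size is justified by feasibility and planning needs, the mean-change analysis is called exploratory, and variance estimates for the next trial are already planned. That limits the consequence but does not make the stated power correct.

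**Conclusion.** The claim is wrong as written. At 26 complete datasets and two-sided 5%, the within-participant effect detectable with 90% and 80% power is 0.66 and 0.57 SD, not 0.41 and 0.36. Power at the stated effects is about 52% and 42%, or 65% and 56% if the test is one-sided. This rests on a t-test of one change score per participant. The stated effect is also not the tDCS–sham contrast that the SAP tests.

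Four stronger readings are not supported:

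- A reader might infer that the trial's true detectable difference between arms is about 199 and 172 steps per week (1.326 and 1.145 × 150). Those values assume one period and no adjustment, and the planned analysis may detect smaller differences.
- A reader might infer that an SD of 21.4 steps per day is itself wrong. The documents give no baseline step count or SD against which to judge it; they show only that its source and unit cannot be checked.
- A paired test with n = 64 gives 0.412 and 0.356, so one might suppose that 32 was doubled. Nothing in the documents says so.
- A reader might conclude that the trial is too small. Its size does not rest on this calculation.

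Severity is minor to moderate. Confidence in the arithmetic is high.

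**What to change.** 1. Correct or withdraw both the standardized effects 0.41 and 0.36, which cover all functional endpoints, and the derived 62 and 54 steps per week. Removing only the step figures would leave the faulty sentence in place.
2. If a within-participant figure is kept, give 0.66 SD (90%) and 0.57 SD (80%), for n = 26, two-sided 5% and a single change score, and say that it is not a difference between arms.
3. State the detectable tDCS–sham difference as 1.33 SD (90%) and 1.15 SD (80%) of the change, for 13 per arm, one two-week period and no baseline adjustment. Add that the repeated-measures, baseline-adjusted analysis may detect smaller differences, by an amount that depends on correlations not given.
4. Put any absolute figure in steps per day, and give the source of the SD of 150 and whether it is per day or per week.

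This is wording only. The sample size, endpoint and analysis do not change; the only cost is a less favourable stated figure.
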